**Table 9: Proposed Modified International Working Group Response Criteria for Altering Natural History of MDS**

Category	Response criteria (Responses must last at least 4 weeks)
Complete remission	Bone marrow: $\leq 5\%$ myeloblasts with normal maturation of all cell lines* Persistent dysplasia will be noted*† Peripheral blood‡ Hgb $\geq 11$ g/dL Platelets $\geq 100 \times 10^9/L$ Neutrophils $\geq 1.0 \times 10^9/L$ † Blasts = 0%
Partial remission	All CR criteria if abnormal before treatment except: Bone marrow blasts decreased by $\geq 50\%$ over pretreatment but still $> 5\%$ Cellularity and morphology not relevant
Marrow CR†	Bone marrow: $\leq 5\%$ myeloblasts and decrease by $\geq 50\%$ over pretreatment† Peripheral blood: if HI responses, they will be noted in addition to marrow CR†
Stable disease	Failure to achieve at least PR, but no evidence of progression for $> 8$ wks
Failure	Death during treatment or disease progression characterized by worsening of cytopenias, increase in percentage of bone marrow blasts, or progression to a more advanced MDS FAB subtype than pretreatment
Relapse after CR or PR	At least 1 of the following: Return to pretreatment bone marrow blast percentage Decrement of $\geq 50\%$ from maximum remission/response levels in granulocytes or platelets Reduction in Hgb concentration by $\geq 1.5$ g/dL or transfusion dependence
Cytogenetic response	Complete: Disappearance of the chromosomal abnormality without appearance of new ones Partial: At least 50% reduction of the chromosomal abnormality
Disease progression	For patients with: Less than 5% blasts: $\geq 50\%$ increase in blasts to $> 5\%$ blasts 5%-10% blasts: $\geq 50\%$ increase to $> 10\%$ blasts 10%-20% blasts: $\geq 50\%$ increase to $> 20\%$ blasts 20%-30% blasts: $\geq 50\%$ increase to $> 30\%$ blasts Any of the following: At least 50% decrement from maximum remission/response in granulocytes or platelets Reduction in Hgb by $\geq 2$ g/dL Transfusion dependence

Source: (Cheson, et al. 2006)

AML = acute myeloid leukemia; CR = complete remission; DFS = disease-free survival; FAB = French-American-British; Hgb = hemoglobin; HI = hematologic improvement; MDS = myelodysplastic syndromes; PFS = progression-free survival; PR = partial remission.

Note: Deletions to International Working Group (IWG) response criteria are not shown.

Note: To convert hemoglobin from g/L to g/dL, divide g/L by 10.

\*Dysplastic changes should consider the normal range of dysplastic changes (modification).

†Modification to IWG response criteria (Cheson, et al. 2003)

‡In some circumstances, protocol therapy may require the initiation of further treatment (e.g., consolidation, maintenance) before the 4-week period. Such subjects can be included in the response category into which they fit at the time the therapy is started. Transient cytopenias during repeated chemotherapy courses should not be considered as interrupting durability of response, as long as they recover to the improved counts of the previous course.

**Table 10: Proposed Modified International Working Group Response Criteria for Hematologic Improvement**

Hematologic improvement*	Response criteria (Responses must last at least 8 weeks)†
Erythroid response (pretreatment, < 11 g/dL)	Hgb increase by $\geq 1.5$ g/dL Relevant reduction of units of RBC transfusions by an absolute number of at least 4 RBC transfusions/8 wk compared with the pretreatment transfusion number in the previous 8 wk. Only RBC transfusions given for a Hgb of $\leq 9.0$ g/dL pretreatment will count in the RBC transfusion response evaluation†
Platelet response (pretreatment, < $100 \times 10^9/L$ )	Absolute increase of $\geq 30 \times 10^9/L$ for patients starting with $> 20 \times 10^9/L$ platelets Increase from $< 20 \times 10^9/L$ to $> 20 \times 10^9/L$ and by at least 100%†
Neutrophil response (pretreatment, < $1.0 \times 10^9/L$ )	At least 100% increase and an absolute increase $> 0.5 \times 10^9/L$ †
Progression or relapse after HI‡	At least 1 of the following: At least 50% decrement from maximum response levels in granulocytes or platelets Reduction in Hgb by $> 1.5$ g/dL Transfusion dependence

Source: (Cheson, et al. 2006)

Hgb = hemoglobin; HI = hematologic improvement; RBC = red blood cell.

Note: Deletions to the International Working Group (IWG) response criteria are not shown.

Note: To convert hemoglobin from g/L to g/dL, divide g/L by 10.

\* Pretreatment counts averages of at least 2 measurements (not influenced by transfusions)  $\geq 1$  week apart (modification).

† Modification to IWG response criteria (Cheson, et al. 2003)

‡ In the absence of another explanation, such as acute infection, repeated courses of chemotherapy (modification), gastrointestinal bleeding, hemolysis, and so forth. It is recommended that the 2 kinds of erythroid and platelet responses be reported overall as well as by the individual response pattern.

## 10.9. Pharmacokinetic Assessments

### 10.9.1. Blood Sample Collection and Pharmacokinetic Measurements During Dose Escalation

Serial blood samples will be drawn before and after dosing with AG-221 in order to determine circulating plasma concentrations of AG-221 (and, if technically feasible, the metabolite of AG-221, AGI-16903). The blood samples will also be used for the determination of 2-HG and  $\alpha$ -KG, for evaluation of cholesterol, and 4 $\beta$ -OH-cholesterol levels (see Section 10.10.1 and Section 10.11).

For the first 3 subjects enrolled in a cohort during the dose escalation phase and the first 15 subjects enrolled in each arm of Part 1 Expansion (unless approved by the Medical Monitor to omit the assessment), a single dose of AG-221 will be administered on Day -3 (i.e., 3 days prior to their scheduled C1D1 dose). Blood samples will be drawn prior to the single-dose administration of AG-221 (within 30 minutes) and at the following time points after administration: 30 ( $\pm 10$ ) minutes and 1, 2, 3, 4, 6, 8, and 10 hours, ( $\pm 10$  minutes), and 24, 48, and 72 hours ( $\pm 1$  hour). After 72 hours of blood sample collection, subjects will begin oral daily dosing of AG-221 (i.e., C1D1). The PK/PD profile from Day -3 through Day 1 is optional for additional subjects enrolled in the dose escalation phase (i.e., for any subjects beyond the 3 initial

subjects enrolled in a cohort) and may be required for subjects beyond the initial 15 enrolled in each of the expansion arms based on Medical Monitor decision.

All subjects in the dose escalation phase and Part 1 Expansion will undergo 10-hour PK/PD sampling on C1D15, C2D1, and C4D1. For this profile, one blood sample will be drawn immediately prior to (within 30 minutes) that day's first dose of AG-221 (i.e., dosing with AG-221 will occur at the clinical site); subsequent blood samples will be drawn at the following time points after dosing: 30 minutes, and 1, 2, 3, 4, 6, 8, and 10 hours ( $\pm 10$  minutes).

Predose blood samples (trough) will be obtained for subjects in the dose escalation phase and Part 1 Expansion on C1D1 (for those subjects who did not undergo the Day -3 sampling), C1D8, C1D22, C2D15, C3D1, C3D15, C5D1 and Day 1 of all cycles through cycle 12 for determination of AG-221 concentrations, as well as 2-HG and  $\alpha$ -KG concentrations (see [Section 10.10.1](#)). Additionally, blood samples will be drawn at the End of Treatment Visit (EOT).

For subjects in the Phase 2 portion of the trial, blood samples for PK assessment will be drawn on C1D1 predose (within 30 minutes) and post-dose at the following time points: 2, 4, 6, and 8 hours ( $\pm 10$  minutes); and on C2D1 predose (within 30 minutes) and post-dose at the following time points: 2, 4, 6, and 8 hours ( $\pm 10$  minutes). Additional blood samples for PK/PD assessments will be drawn on C1D2, C2D2, and C3D1 predose (within 30 minutes). In addition, blood samples for PK/PD assessments will also be drawn at the EOT visit.

When the timing of a blood sample coincides with the timing of an ECG measurement, the ECG will be completed before the collection of the blood sample (within 10 minutes). The timing of blood samples drawn for AG-221 concentration determination may be changed if the emerging data indicates that an alteration in the sampling scheme is needed to better characterize AG-221's PK profile.

See also [Table 4](#) and [Table 5](#) for the schedule of PK/PD assessments.

### 10.9.2. Urine Collection

For the first 3 subjects enrolled in a cohort during the dose escalation phase and the first 15 subjects enrolled in each arm of Part 1 Expansion (unless approved by the Medical Monitor to omit the assessment), urine will be collected on Day -3 prior to and over the first 72 hours following a single dose of AG-221 to provide a preliminary estimate of the extent to which AG-221 (and, if technically feasible, the potential metabolite of AG-221, AGI-16903) is eliminated unchanged in the urine. Samples also will be analyzed for 2-HG and  $\alpha$ -KG concentrations and for urinary creatinine concentration (see [Section 10.10.2](#)). Urine samples are not required for subjects enrolled in the Phase 2 portion of the trial.

Five urine collections will be obtained during this 72-hour period. An initial urine collection will be obtained prior to AG-221 dosing (at least 20 mL). Subsequent collections will be obtained at the time of the 10-, 24-, 48- and 72-hour blood draws ( $\pm 1$  hour). Additionally, a urine collection (at least 20 mL) will occur at the End of Treatment Visit.

The serial urine sampling from Day -3 through Day 1 is optional for additional subjects enrolled in the dose escalation phase (i.e., for any subjects beyond the 3 initial subjects enrolled in a cohort) and for subjects beyond the initial 15 enrolled in each of the Part 1 Expansion arms. For

subjects in the dose escalation phase and Part 1 Expansion who do not have the Day -3 through Day 1 serial urine sampling, a predose urine sample is required on C1D1.

Urine samples are not required for subjects enrolled in the Phase 2 portion of the trial.

The volume of each collection will be measured and recorded and sent to a central laboratory for determination of the urinary AG-221 concentration.

## **10.10. Pharmacodynamic Assessments**

### **10.10.1. Blood Samples**

Serial blood samples will be drawn before and after dosing with AG-221 in order to determine circulating concentrations of 2-HG and  $\alpha$ -KG. Samples collected for PK assessments also will be used to assess 2-HG and  $\alpha$ -KG levels (see [Section 10.9.1](#)). In addition, subjects will have blood drawn for determination of 2-HG and  $\alpha$ -KG levels at the screening assessment.

The timing of blood samples drawn for 2-HG and  $\alpha$ -KG concentration determination may be changed if the emerging data indicate that an alteration in the sampling scheme is needed to better characterize the 2-HG and/or  $\alpha$ -KG response to AG-221 treatment.

Bone marrow also will be assessed for 2-HG and  $\alpha$ -KG levels, see [Section 10.7](#).

### **10.10.2. Urine Samples**

Urine will be collected from subjects in the dose escalation phase and Part 1 Expansion phase before and after dosing with AG-221 for the determination of concentrations of 2-HG and  $\alpha$ -KG. Samples collected for PK assessments on Day -3 through Day 1 will also be used to assess 2-HG and  $\alpha$ -KG levels (see [Section 10.9.2](#)). In addition, subjects will have urine sample collected for determination of 2-HG and  $\alpha$ -KG levels at the screening assessment and the End of Treatment visit.

In addition, for all subjects, a urine collection will occur prior to dosing on Day 15 of Cycle 1 and on Day 1 of Cycle 2 through at least Cycle 12, and every 3 cycles thereafter. At least 20 mL of urine will be collected for each sample.

Urine samples are not required for subjects enrolled in the Phase 2 portion of the trial.

The volume of each collection will be measured and recorded and sent to a central laboratory for determination of urinary 2-HG and  $\alpha$ -KG concentration. An aliquot from each collection will be analyzed for urinary creatinine concentration.

## **10.11. Evaluation of Cholesterol and 4 $\beta$ -OH-Cholesterol**

For subjects in the dose escalation phase and Part 1 Expansion, serial blood samples will be drawn to obtain plasma cholesterol and 4 $\beta$ -OH-cholesterol levels as a potential CYP3A4 induction marker. A subset of samples collected for PK assessments also will be used to assess cholesterol and 4 $\beta$ -OH-cholesterol levels (see [Section 10.9.1](#)). Specifically, samples obtained at screening and on Day -3 predose (within 30 minutes), and 24, 48, and 72 hours ( $\pm$ 1 hour) will be assessed for cholesterol and 4 $\beta$ -OH-cholesterol levels. Samples collected predose on Days 1, 8, 15 and 22 of Cycle 1, Days 1 and 15 of Cycles 2 and 3, and Day 1 of every cycle through at least

Cycle 12, and samples obtained at the End of Treatment visit also will be assessed for cholesterol and 4 $\beta$ -OH-cholesterol levels.

Samples for plasma cholesterol and 4 $\beta$ -OH-cholesterol levels are not required for subjects enrolled in the Phase 2 portion of the trial.

#### **10.12. Sample Processing, Storage, and Shipment**

Instructions for the processing, storage and shipment of all study samples for central analysis will be provided in a separate study manual.

## 12. STATISTICAL METHODS

### 12.1. Sample Size Estimation

[figure not shown]
Based on the planned dose escalation scheme (see [Section 9.7](#)), it is estimated that approximately a minimum of 291 subjects may be enrolled in the study.

Assuming that identification of the MTD/MAD requires the evaluation of 13 dose levels/schedules of AG-221 with up to 5 subjects per dose level, with the exception that the MTD requires 6 subjects, then 66 subjects will be enrolled during the dose escalation part of the study. Additional subjects may be needed for cohort expansion during dose escalation, for the replacement of subjects who are not evaluable for PK/PD, safety, or clinical activity, or for evaluation of alternative dosing regimens other than the planned escalation scheme or the MTD, to optimize the RP2D and regimen(s). As of April 2015, 5 dose levels (ranging from 30 mg to 150 mg) have been evaluated in the BID schedule and 8 dose levels (ranging from 50 mg to 650 mg) have been evaluated in the QD schedule.

Four cohorts of approximately a minimum of 25 additional subjects in specific hematologic malignancy subsets (total a minimum of 100 subjects) will be enrolled in Part 1 Expansion of the study. The Phase 2 will enroll approximately 125 subjects with relapsed or refractory AML with an IDH2 mutation.

[Figure 8](#) present the probability of escalation from a lower dose to the next higher dose, for a range of true rates of DLT, in the standard 3+3 dose-escalation design. For example, if the true DLT rate were 0.20 (20%), then the chance of dose escalation would be approximately 0.70 (70%).

**Figure 8: Probability of Dose Escalation for the 3+3 Design**

To ensure acceptable toxicity at the MTD or other doses and regimens that may be used in further studies, approximately 25 additional subjects will be accrued into each of 4 arms in Part 1

Expansion. Based on a sample size of 25 subjects within each arm, there is 93% probability of detecting 1 or more AEs with an underlying rate of 10%, and 72% probability of detecting 1 or more AEs with an underlying rate of 5%.

### Phase 2:

An overall objective response rate (ORR, see [Section 12.5.7](#)) of at least 33.6% in 125 subjects (at least 42 responses in 125 subjects) will result in an exact binomial 95% CI with a lower bound greater than 25%, which is clinically meaningful in this setting and exceeds the ORR expected with available therapies ([Roboz, et al. 2014](#)). If 42 responses in 125 subjects are observed (33.6% observed ORR), the 95% CI will be (25.4%, 42.6%). This will be considered as evidence of clinically significant activity of AG-221.

Additional subjects may be needed for the replacement of subjects who are not evaluable for PK/PD, safety, and/or clinical activity, or for evaluation of alternative dosing regimens.

## 12.2. Populations for Analysis

The following subject populations (i.e., analysis sets) will be evaluated and used for presentation of the data:

- Full Analysis Set (FAS): All subjects who were enrolled and received at least one dose of study treatment. Subjects will be classified according to the assigned dose level and schedule. The FAS is the primary analysis population for efficacy and will be the default analysis set for all analyses, unless otherwise specified.
- Dose Determining Set (DDS): All dose escalation subjects who either had a DLT during Cycle 1, or who completed at least 75% of their planned Cycle 1 doses (21 out of 28 days) and were considered by the Clinical Study Team to have had sufficient safety data available to conclude that a DLT did not occur during Cycle 1.
- Safety Analysis Set (SAS): All subjects who were enrolled and received at least one dose of study treatment. Subjects will be classified according to the treatment received, where treatment received is defined as the assigned dose level/schedule if it was received at least once, or the first dose level/schedule received if assigned treatment was never received. The SAS will be the primary set for the analysis of safety data.
- Evaluable Analysis Sets
  - Evaluable Analysis Set (EAS): All subjects in the FAS for whom the baseline response assessment and at least one post baseline response assessment at Day 28 or later are available and evaluable.
  - Central Evaluable Analysis Set (CEAS): All subjects in the FAS for whom the baseline response assessment and at least one post baseline response assessment at Day 28 or later are available and evaluable by central independent review.

Results of the potential clinical activity of AG-221 will be primarily based on the FAS. Additional efficacy analyses will be produced for the EAS and CEAS.

- Pharmacokinetic Analysis Set (PAS): All subjects who have at least one blood sample providing evaluable PK data for AG-221.

### **12.3. Procedures for Handling Missing, Unused, and Spurious Data**

No imputation will be performed for missing data elements.

When tabulating AE data, partial dates will be handled as follows. If the day of the month is missing, the onset day will be set to the first day of the month unless it is the same month and year as study treatment. In this case, in order to conservatively report the event as treatment emergent, the onset date will be assumed to be the date of treatment. If the onset day and month are both missing, the day and month will be assumed to be January 1, unless the event occurred in the same year as the study treatment. In this case, the event onset will be coded to the day of treatment in order to conservatively report the event as treatment emergent. A missing onset date will be coded as the day of treatment.

For the purposes of reporting, subjects continuing to receive study drug will have time-to-event data (e.g., duration of response and EFS) censored at the date of last documented disease assessment prior to the data cutoff date. Further details of censoring rules will be documented in the statistical analysis plan.

Subjects who have disease progression and continue to receive treatment after progression will be considered as having documented progressive disease at the time of first progression and will be counted as progressive disease at that time in primary efficacy analyses. All response assessments occurring after documented progression will be listed and analyzed separately.

Subjects who discontinue AG-221 treatment to receive HSCT will remain on study and will be followed until documented disease progression or end of study.

Subjects with a best overall response of 'Unknown' or 'Not Evaluable' will be considered non-responders in estimating response rates in the efficacy analysis.

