### **10.8.3. Assessment of Response Criteria**

Evidence supports that cancer-associated IDH mutations block normal cellular differentiation and promote tumorigenesis via the abnormal production of 2-HG, a potential oncometabolite (Figure 3). AG-221 may produce antitumor effects by reversing the differentiation block induced by the IDH2 mutations and promoting appropriate cellular differentiation.

The response pattern seen with such mechanism of action may extend beyond the typical time course of responses seen with cytotoxic agents, and can generate a clinical response after an initial increase in the number of immature monocytes or blast cells, and increase in cellularity in the bone marrow, onset of cytopenia after initial rise in platelets, or appearance of differentiation-like syndrome.

Standard assessment criteria developed based on the experience from the cytotoxic chemotherapeutic agents may not provide a complete and accurate response assessment for this novel class of IDH2 inhibitors. Therefore, in the setting where a subject's assessment shows signs similar to progression within the first 2 cycles, caution should be exercised in discontinuing study drug, and a discussion with the Medical Monitor is required, especially in situations where the subject's clinical condition is stable as supported by, but limited to, absence of signs and symptoms of rapid deterioration indicating disease progression and/or general condition is stable or improving.

**Note** that for subjects enrolled in the Phase 1 portion of the trial, the C1D15 bone marrow evaluation should not be used to determine study treatment continuation status in any subject.

Subjects who experience progression of disease (PD) per the applicable response criteria should have assessment of the disease repeated 28 days later in order to confirm PD with option of continuing treatment as described above while awaiting for confirmation. If repeat evaluation confirms PD, subjects will discontinue study treatment and proceed to the survival follow-up phase (see Table 6 for general guidance).

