**Table 8: Criteria for Stable Disease and Progressive Disease for Acute Myelogenous Leukemia**

Category	Response criteria
Stable disease	Failure to achieve a response and not meeting the criteria for disease progression
Disease progression (defined only for subjects who have previously attained PR or SD)	
Progression should be confirmed by 2 consecutive assessments separated by at least 1 month.
 
Development of new biopsy-confirmed extramedullary disease since last disease evaluation
 
The date of progressive disease is defined as the first date of progression.
 
Progression is defined as the following:
 
For patients with 5 to 67% bone marrow blasts at nadir:
 
 
- a >50% increase in bone marrow blast count percentage from the nadir and that is <math>\geq 20\%</math>.
 
 
For patients with <math>\geq 67\%</math> bone marrow blasts at nadir:
 
 
- a doubling of the nadir absolute peripheral blood blast count and the final absolute peripheral blood blast count is <math>> 10 \times 10^9/L</math>.
 

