10.2. Analysis of Primary Efficacy Endpoint

The primary efficacy endpoint of ORR is defined as the rate of responses including CR, CRi, CRp, PR, mCR (for MDS) and MLFS (for AML) by investigator assessment. The ORR will be summarized by the percentage of responses primarily in the FAS with 2-sided exact binomial 95% CI.

Response will also be summarized by the best objective response following the hierarchical order of CR, CRi/CRp, PR, mCR/MLFS, stable disease, relapse/progressive disease/failure, and not evaluable (NE).

An observed ORR in the pivotal Phase 2 R/R AML FAS subjects with the lower bound of the exact binomial 95% CI greater than 25% is deemed clinically meaningful and exceeds the expected ORR with other available therapies. This will be considered as evidence of clinically significant activity of AG-221. The analyses in the combined Phase 1/2 R/R AML on total daily dose of 100mg utilize larger population and thus provide robust estimate of ORR to better describe the clinical activity of AG-221.

To assess the robustness of the primary analysis, the following sensitivity analyses will be performed:

- (1) ORR in the EAS for the combined Phase 1, Phase 2, and the combined Phase 1/2;

- (2) The ORR assessed by Independent Response Adjudication Committee (IRAC) in the FAS for Phase 1, Phase 2, and the combined Phase 1/2 R/R AML.

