13. CHANGES TO THE STATISTICAL ANALYSES SECTION OF THE PROTOCOL

- The cut-off date of 01 Sep 2017 for the MAA submission was added.
- Use ‘response’ instead of ‘remission’ for CR, PR, CRR, etc.
- Add secondary endpoints of CR/CRi/CR_p rate, CR/CR_h rate, DOCR/CR_h, and TTCR/CR_h.

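### Protocol 12.3 keeps responses after documented progression out of the primary efficacy analyses, but SAP 10.2 defines the primary ORR with no cut-off at progression and SAP 13 declares no change

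*Protocol*

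**What the plan says.** **Protocol 12.3.** A subject who progresses and stays on treatment has PD dated at the first progression and "will be counted as progressive disease at that time in primary efficacy analyses". Of what follows, it says: "All response assessments occurring after documented progression will be listed and analyzed separately". ORR is the primary efficacy endpoint (Synopsis, Statistical methods), so the rule governs ORR.

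**Protocol Table 8 and 10.8.3.** For AML, "Progression should be confirmed by 2 consecutive assessments separated by at least 1 month", and "The date of progressive disease is defined as the first date of progression". Table 8 defines progression only for subjects who have already reached PR or SD. Section 10.8.3 says that the drug "can generate a clinical response after an initial increase in the number of immature monocytes or blast cells", and that subjects with PD "should have assessment of the disease repeated 28 days later in order to confirm PD". Under Table 6, treatment goes on if the repeat shows SD, PR or CR, and stops if it confirms PD. A note below Table 6 still lets subjects with progressive disease continue, with Medical Monitor approval. In Phase 2, relapse or PD is also one of the listed triggers for raising the dose from 100 to 200 mg QD (protocol 9.7.2.1).

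**SAP 10.2.** ORR is the rate of CR, CRi, CRp, PR and mCR/MLFS by investigator assessment. Response is also "summarized by the best objective response following the hierarchical order of CR, CRi/CRp, PR, mCR/MLFS, stable disease", with relapse and PD below that. No response window is given. The ORR sensitivity analyses cover the EAS and the IRAC assessment.

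**SAP 10.3.1.4.** Table 3 note 1 treats a single PD or relapse that is followed by response as not evaluable. A sensitivity analysis restores that first PD. Both are written for DOR.

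**SAP 13.** Three changes from the protocol are listed: an added data cut-off, a change of terms ("Use ‘response’ instead of ‘remission’ for CR, PR, CRR, etc"), and added secondary endpoints.

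**The concern.** The protocol has a stated rule on which responses count toward the primary endpoint. The SAP section from which that endpoint will be programmed does not carry it, and the SAP's list of changes does not withdraw it. Responses after PD are foreseeable here, because treatment may continue past PD and PD may prompt a dose increase. The FAS is analysed by assigned treatment (SAP 5.2.1), so a first response on the raised dose would fall in the Phase 2 ORR unless a rule keeps it out.

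Protocol 12.5.7 calls Phase 2 the pivotal part of the study. The only stated criterion for its primary endpoint is an exact 95% lower bound above 25%. If two programmers can follow the two documents in good faith and obtain different responder counts, that criterion is not fully specified. The CR rate has the same gap.

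**Working it through.** **Step 1. Apply each document to each sequence.**

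| Sequence | Protocol 12.3 with Table 8 | SAP 10.2 |
|---|---|---|
| Response, later PD | Response | Response |
| Single PD not confirmed on repeat, then response | Response if 12.3 means confirmed PD; not a response if any first PD counts | Response: no cut-off, and Table 3 note 1 (for DOR) points the same way |
| Confirmed PD, then first response on continued treatment or a raised dose | Not counted; analysed separately | Nothing excludes it |

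Only the third row is a clear divergence. The second is an ambiguity inside 12.3. SAP 5.1 does exclude late data in one case, restart of study drug after HSCT, which does not cover treatment continued past PD.

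**Step 2. Reproduce the plan's figure.** Inputs: n = 125, threshold 42, criterion 25% (protocol 12.1 and 12.5.7; SAP 10.2). For x responders the exact two-sided 95% limits are

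- lower = 2.5% quantile of Beta(x, n − x + 1)
- upper = 97.5% quantile of Beta(x + 1, n − x)

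For x = 42, Beta(42, 84) gives 25.40% and Beta(43, 83) gives 42.60%. This matches the interval in protocol 12.1. The smallest x with a lower bound above 25% is 42.

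**Step 3. Move subjects across the line.** One subject is 1/125 = 0.8 percentage points.

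| Responders | ORR | Lower bound | Above 25%? |
|---|---|---|---|
| 44 | 35.2% | 26.9% | yes |
| 42 | 33.6% | 25.4% | yes |
| 41 | 32.8% | 24.7% | no |
| 39 | 31.2% | 23.2% | no |

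A count of 42 cannot lose one subject. A count of 44 can lose two (44 − 2 = 42) but not three (44 − 3 = 41).

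**Step 4. Illustrate the effect on the chance of meeting the criterion.** Assume a true ORR of 36.4% with no cut-off at progression. This borrows the preliminary rate in 44 subjects at 100 mg QD (protocol 7.1.3); the documents do not say which counting rule that rate used. Let f be the share of subjects whose only response follows confirmed PD. The documents do not give f, so a range is shown. The chance is P(X ≥ 42) for X ~ Binomial(125, 0.364 − f).

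| f | Chance |
|---|---|
| 0 | 0.770 |
| 1% | 0.694 |
| 2% | 0.608 |
| 3% | 0.515 |
| 5% | 0.329 |
| 10% | 0.045 |

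An f of 1% is 1.25 subjects of 125 on average.

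**The case against.** **The SAP's silence does not revoke the protocol.** A reader might infer that the SAP takes the best response at any time. It does not say so. The hierarchy belongs to an additional summary of response categories, and the absence of an entry in SAP 13 fits a rule that still applies as well as it fits an undeclared change. This stands in part: counting responses after PD is an inference from a definition without a window. But 10.2 is the operative text for ORR, and it neither states the 12.3 rule nor refers to it.

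**The drug's described pattern is not the problem group.** A reader might also infer that a subject with a blast rise at C2D1 and a later CR is a non-responder under the protocol and a responder under the SAP. The documents do not support this. Table 8 needs two consecutive assessments at least a month apart and a prior PR or SD, and C2D1 is the first scheduled Phase 2 response assessment after baseline. The repeat assessment and Table 6 exist for such subjects. The natural joint reading of 12.3 and Table 8 is confirmed PD, dated back to its first assessment. On that reading both documents can count the response. This stands, except that 12.3 does not itself say confirmed.

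**The numbers may be small.** Table 6 directs that treatment stop at confirmed PD and asks for no further assessment; continuing needs approval. And any classification detail can decide a result that sits on its threshold. Both points stand, and they lower the severity.

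**Conclusion.** The two documents are not reconciled on whether a response first documented after confirmed PD counts in the primary ORR. Protocol 12.3 keeps it out, nothing in SAP 10.2 does, and no change is declared. For an unconfirmed PD followed by response, the texts lean toward counting it, but 12.3 needs one word to settle this.

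The size is unknown, because the documents give no count of affected subjects. Each one moves ORR by 0.8 points, and one is decisive only if the count sits at the threshold. The probabilities in the working rest on an assumed f and a borrowed 36.4%; they show sensitivity and are not a forecast. The plan's own threshold and interval are correct.

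This should be fixed, because a stated protocol rule for a pivotal primary endpoint is missing from the analysis text. It is not a fatal flaw: the gap affects a limited group and can be closed by wording.

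**What to change.** Analysis text only; no treatment rule changes.

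- **SAP 10.2:** carry over protocol 12.3 read with Table 8. The response window for ORR and CRR ends at a PD or relapse confirmed per protocol Tables 7 and 8, dated at its first assessment. An unconfirmed PD followed by response does not end the window. A response first documented after confirmed PD is excluded from the primary ORR and listed separately.
- **Protocol 12.3:** add the word confirmed to the progression that triggers the rule.
- **SAP 13:** record the rule.
- **Sensitivity:** report one ORR that counts best response regardless of progression and, optionally, one whose window ends at any first PD. Give the number of subjects whose status differs from the primary analysis.

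The cost is a few sentences and one table. The downside is that the primary ORR may come out slightly below the unrestricted figure; the sensitivity analysis shows by how much.
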